2.3 Exploratory Objectives & Endpoints

2.3.1 Objectives:

The exploratory objectives of this study are to:

- To explore the relationship between drug exposure, pharmacodynamics, efficacy, and safety of each OncoTreat-prioritized agent. Pharmacodynamic response will be evaluated by comparing the master regulator signature of a given subject's tumor using VIPER analysis, comparing pre-treatment and on-treatment tumor samples. The changes in master regulator activity between these two samples will be compared to that predicted from cell-based and PDX-based treatment studies.
- To assess whether the master regulator signature, using VIPER analysis, in a given subject's tumor changes in response to standard-of-care treatment by comparing initial and secondary biopsies collected for each subject before and after one or two lines of systemic therapy (chemotherapy or clinical trial). These data will be used to determine whether the predicted sensitivity of a patient's tumor to the first-or second-line therapy that they receive is predictive of the actual clinical outcomes that are observed during treatment.
- Using the same data as in the bullet point above, assess the frequency with which chemotherapy treatments alter the predicted sensitivity of tumors to other OncoTreat-prioritized agents (p-value $< 1 \ge 10^{-5}$).
- To compare the standard-of-care clinical DNA mutation analysis results with matched master regulator activity profiles to correlate any clinically actionable genomic information with the top OncoTreat-prioritized drugs.
- To evaluate the feasibility of using the OncoTreat technology on peripheral blood circulating tumor cells (CTCs) by comparing master regulators generated from CTCs to those obtained from tumor tissue in matched pre- and on-treatment samples with an OncoTreat-informed agent.
- To identify associations between master regulator profiles and additional clinical, epidemiological, physiological, imaging, or molecular features of the subject or subject's tumor.
- To identify potential biomarkers, beyond the master regulator signature, using additional genomic, RNA, protein, and imaging platforms that are predictive or prognostic of response to each OncoTreat-prioritized agent (p-value $< 1 \times 10^{-5}$).

2.3.2 Endpoints:

Exploratory endpoints of interest include:

- Pharmacodynamic response will be assessed by determining the differentially activated and repressed master regulator proteins between the pre-treatment (second) biopsy and the on-treatment (third) biopsy, and comparing these changes to those predicted by OncoTreat using a modified gene set enrichment analysis with a threshold Fasle Discovery Rate of p = 0.05.
- Paired-sample VIPER analysis using Master Regulator profiles from the first and second biopsies.

- The fraction of drugs predicted for each patient using the first biopsy that are still predicted in the second biopsy.
- The DIGGIT algorithm will be used to associate DNA alterations, found from enomic profiling using next-generation sequencing (NGS) assays such as CCCP or Foundation One, with master regulator activity.
- Percentage of OncoTreat-prioritized agents (p-value < 1 x 10⁻⁵) that overlap between tumor biopsy specimens and peripheral blood CTCs.
- Relationship between biomarkers in blood and tumor tissue and efficacy, safety, PK, or other biomarker endpoints.

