Step 4. Candidate drug selection. By integrating the above datasets, we can identify drugs that shut down the activity of the specific MRs active in an individual patient's profile. This analysis is integrated across the top 50 MRs for each patient. Successful matches are those drugs that reverse the activity of many or all of these top 50 MRs.

We have performed a preliminary analysis of the OncoTreat methodology on existing pancreatic cancer tumor profiles and found at least one matching drug for 85% of patients (using a conservative threshold FDR of 1×10^{-5}). Moreover, at least 50% of patients have 5 or more matched drugs using the OncoTreat approach, providing an opportunity to screen multiple candidate agents for a given patient using patient-derived models such as PDXs and organoids.

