4.4 Tumor Biopsies

A tissue sample, from either the primary or metastatic site, will be obtained from all treatmentnaïve subjects at the time of initial presentation. This biopsy, therefore, will serve both diagnostic and research purposes prior to initiation of first-line chemotherapy. Tumor tissue acquision, handling, and processing are described in the laboratory manual.

Subjects for whom an OncoTreat-prioritized agent is identified will undergo a repeat biopsy prior to starting the study drug. This will confirm no change in master regulator profile, which is not expected, and that the OncoTreat-prioritized agent identified from the pre-treatment sample is no different than the agent identified now following treatment with chemotherapy.

The window for each biopsy is outlined in the study calendar (Section 9).

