5.1 Inclusion Criteria

In order to be eligible for participation in this trial, the subject must:

- Be willing and able to provide written informed consent for the trial.
- Age ≥ 18 years of age on day of signing informed consent.
- Have histologically or cytologically confirmed diagnosis of pancreatic ductal adenocarcinoma.
- Have a predicted life expectancy of greater than 3 months.
- Have measurable disease based on RECIST v1.1.
- Have a performance status of 0 or 1 using the ECOG Performance Scale
- Have documented radiographic or clinical progression to or documented intolerance to 5-FU- or gemcitabine-based systemic therapy for locally advanced, unresectable or metastastic disease. Patients for whom targeted therapy.
- MSI-H/dMMR or NTRK-fusion positive tumors
 - Subjects must have received prior treatment with approved drugs for tumors harboring these aberrations.
- Have a negative urine or serum pregnancy test within 72 hours prior to receiving the first dose of study medication (female subjects of childbearing potential). If the urine test is positive or cannot be confirmed as negative, a serum pregnancy test will be required.
- Be willing to use an adequate method of contraception for the course of the study through 120 days after the last dose of study medication (male and female subjects of childbearing potential).
- Demonstrate adequate organ function as defined below in Table 5.

Table 5Adequate Organ Function Laboratory Values

	0	e e
System		Laboratory Value

Hematological	
Leukocytes	≥2,000 /mcL
Absolute neutrophil count (ANC)	≥1,500 /mcL
Platelets	≥100,000 /mcL
Hemoglobin	≥9 g/dL without transfusion or EPO
	dependency within 7 days
Renal	
Creatinine OR	\leq 1.5 X upper limit of normal (ULN) OR
Measured or calculated ^a creatinine	\geq 60 mL/min for subject with creatinine levels
clearance (GFR can also be used in	>1.5 X institutional ULN
place of creatinine or CrCl)	
Hepatic	
Total bilirubin	$\leq 2 \text{ mg/dL}$ or direct bilirubin $\leq \text{ULN}$ for those
	with total bilirubin >2 X ULN
	Subjects with Gilbert Syndrome will be
AST (SCOT) and ALT (SCDT)	eligible if total bilirubin is $<3.0 \text{ mg/dL}$
ASI (SGOI) and ALI (SGPI)	<2.5 X ULN OR <5 X ULN for subjects with liver metastases
Albumin	>3.0 mg/dL
Coagulation	
Coagulation	
INR or PT	≤1.5 X ULN unless subject is receiving
aPTT	anticoagulant therapy as long as PT or aPTT
	is within therapeutic range of intended use of
	anticoagulants

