- b. Subjects who discontinue study treatment without documented disease progression should continue to be monitored for disease by radiologic imaging every 8 weeks (±7 days) until (1) the start of new anti-cancer treatment, (2) disease progression, (3) death, or (4) the end of the study, whichever occurs first.
- c. Informed consent will include consent for correlative studies including biopsies and serum collections.
- d. For women of reproductive potential, a negative pregnancy test should be performed within 72 hours prior to first dose of trial treatment. Pregnancy tests (serum and/or urine) should be repeated if required by local guidelines.
- e. Laboratory screening tests should be performed within 14 days prior to first dose of study treatment. For all subjects, unresolved abnormal labs resulting in drug-related AEs should be followed until resolution.
- f. All subjects will be tested for HIV, HBV, and HCV prior to enrollment. Those who are positive for HIV, untreated active Hepatitis B, and dual infection with HBV/HCV will be excluded.
- g. Tumor imaging at screening: Imaging will be performed within 28 days prior to the first dose of OncoTreat-prioritized drug. Imaging should include CT chest, abdomen, and pelvis or MRI if CT is clinically contraindicated.
- h. The first on-study tumor imaging will be performed after 8 weeks (±7 days) of treatment and will continue every 8 weeks (±7 days) thereafter (or more frequently if clinically indicated). Timing of imaging follows calendar days and should not be adjusted due to dose interruptions. The same imaging technique, acquisition, and processing parameters for a subject should be used throughout the trial if possible.
- i. Subjects without confirmed PD who discontinue treatment will have imaging performed at the time that study treatment is discontinued (i.e. date of discontinuation ± 4 week window). If a scan was obtained within 4 weeks prior to discontinuation of treatment, then imaging at treatment discontinuation is not required. Subjects who discontinue treatment after confirmed PD will not need further imaging performed during the follow-up period.
- j. Following disease progression/intolerance to standard of care therapy, a fresh tumor biopsy (primary or metastatic site) is required to be performed after the last dose of systemic therapy. OncoTreat analysis will confirm the master regulator profile and the recommended OncoTreat-informed drug.

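### Two exploratory paired-biopsy analyses need rewording: the prediction question is tied to subjects selected partly on the outcome, and the drug-retention fraction falls below 100% from resampling alone

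*Combined protocol and SAP*

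**What the plan says.** **Prediction question.** The second exploratory objective in Section 2.3.1 concerns change in the master regulator signature, studied by "comparing initial and secondary biopsies collected for each subject before and after one or two lines of systemic therapy". The next sentence reads "These data will be used to determine whether the predicted sensitivity of a patient's tumor to the first-or second-line therapy" and goes on to ask whether that prediction matches the outcome seen on treatment. The grammatical referent is the paired biopsies.

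**Who has a second biopsy.**
- Section 4.4: "Subjects for whom an OncoTreat-prioritized agent is identified will undergo a repeat biopsy prior to starting the study drug".
- Section 9.1, footnote j: "Following disease progression/intolerance to standard of care therapy, a fresh tumor biopsy (primary or metastatic site) is required to be performed". The footnote places it once prior systemic treatment has ended.
- Section 5.1, prior therapy: "Have documented radiographic or clinical progression to or documented intolerance to 5-FU- or gemcitabine-based systemic therapy".
- Section 5.1, fitness: "Have a performance status of 0 or 1 using the ECOG Performance Scale".
- Section 4.1: subjects with no identified or available agent after second-line therapy screen-fail for Part 2 but are still followed for response.

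**Change question.** The third exploratory objective asks how often chemotherapy alters predicted sensitivity to other agents and carries the threshold p < 1 x 10⁻⁵. The matching endpoint in Section 2.3.2 is "The fraction of drugs predicted for each patient using the first biopsy that are still predicted in the second biopsy". A separate endpoint there compares master regulator profiles between the two biopsies.

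**What is not given.** There is no planned test, no reference value for retention without change and no repeat-biopsy agreement figure. Section 10.9, on exploratory endpoints, has a heading but no text. Section 3.4 calls the assay highly reproducible on the basis of frozen versus paraffin tissue.

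**The concern.** **Prediction.** A forecast of first-line outcome needs the biopsy taken before first-line therapy and the outcome. The second biopsy comes after the therapy in question, so it adds nothing to the forecast. Requiring it limits the sample to people whose therapy ended in progression or intolerance and who were then matched and fit enough for Part 2. That selects partly on the outcome being predicted and discards at least half of the subjects.

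**Retention.** Drugs enter this fraction because they scored extremely at the first biopsy, and extreme scores tend to fall back on re-measurement. The two biopsies are also months apart and either may come from the primary or a metastatic site. Some drugs will drop below the cut-off, and others rise above it, with no biological change. Counting losses alone, under an objective that names chemotherapy as the cause, invites the conclusion that chemotherapy altered the predictions.

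At stake is how these results will be read. Section 4.1 describes stability of the tumor's dependencies over time as an idea still to be formally assessed, and the retention fraction is the drug-level part of that assessment.

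**Working it through.** The plan gives no sample size, power or expected value for these analyses, so there is no figure to reproduce.

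**1. Number of subjects**
- Part 1 enrolls 30 (Section 4.2).
- About 15 are expected to reach Part 2 (Synopsis): 30 × 0.50 = 15.
- About 9 are expected to start drug (Section 12): 15 × 0.60 = 9.
- Share with pairs: 9/30 = 30% to 15/30 = 50%. The second biopsy is a screening procedure, so 15 is nearer to the plan's own estimate of Part 2 entry; 9 is the lower end.

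**2. Precision and power.** Suppose prediction is summarized as a correlation with outcome (an assumption; the plan names no statistic). The Fisher-z standard error is 1/√(n − 3). Power for a true correlation of 0.5, two-sided 0.05, is Φ(atanh(0.5) × √(n − 3) − 1.96), with atanh(0.5) = 0.549.

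| n | SE | Power |
|---|---|---|
| 9 | 1/√6 = 0.41 | 27% |
| 15 | 1/√12 = 0.29 | 48% |
| 30 | 1/√27 = 0.19 | 81% |

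These powers allow for sample size only, not for any attenuation from selection.

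**3. Effect of selection.** Assume exponential time to progression with median 6 months (Section 3.1 gives 5–7) and a Spearman correlation of 0.49 with predicted score in all subjects. The windows below are assumptions, not plan rules.

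| Subjects kept (time to progression) | Spearman correlation |
|---|---|
| All | 0.49 |
| Before 18 months | 0.41 |
| 2–18 months | 0.29 |
| 3–12 months | 0.19 |

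Losing long responders costs little. The larger loss comes from also losing early failures.

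**4. Retention when nothing has changed**
- Drugs screened: 121 + 228 = 349 (Section 3.4, Step 3).
- Called share: Section 3.4 reports "at least 50% of patients have 5 or more matched drugs using the OncoTreat approach", so take q = 5/349 = 0.0143. Five is a lower bound on the median; other shares are tried below.
- Let r be the correlation of a drug's score between two biopsies of an unchanged tumor. The documents do not give r.
- Expected retention = P(both scores exceed c)/q, where c is the cut-off that calls a share q.

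| r | Normal scores | Heavy-tailed true scores (t, 3 df) plus normal noise |
|---|---|---|
| 0.80 | 40% | 68% |
| 0.90 | 56% | 79% |
| 0.95 | 69% | 85% |
| 0.99 | 86% | 94% |

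Under normal scores, moving q from 1/349 to 15/349 gives 48–63% at r = 0.90 and 83–88% at r = 0.99.

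**5. Why gains matter.** In this no-change model the two biopsies are exchangeable, so expected gains equal expected losses. At r = 0.90 with normal scores, about 5 × (1 − 0.56) = 2.2 drugs are lost and about 2.2 gained. The retention fraction shows only the losses.

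**The case against.** **The paired data may not be meant as the only data.** The objective mentions initial biopsies, every Part 1 subject has one, and nothing expressly excludes subjects without a second. The Part 1 protocol is not among the documents. This is a fair reason to ask for clarification, but the text as it stands points to the pairs.

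**Selection may be mild.** A reader might infer that most of the outcome range has been removed. The documents do not support that. Entrants include intolerant subjects, a long responder who later progresses can still enter, and best response and time on therapy still vary. With progression before 18 months as the only filter, the assumed correlation falls just from 0.49 to 0.41. This objection stands: the outcome is restricted, not fixed.

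**The retention sizes depend on the model.** This also stands. Heavy-tailed scores cut the artefactual loss to roughly half of that under normal scores, and neither the score distribution nor r is documented. The direction does not depend on this: any imperfect repeat sampling gives expected retention below 100%. The frozen-versus-paraffin comparison does not cover a second biopsy at another time or site.

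**The endpoints are exploratory and there is a companion.** A reader might extend the threshold problem to the paired master regulator profile endpoint. It is not defined by drugs crossing a cut-off, so that part of the point does not reach it. Nor does the plan state 100% as a null or attach a decision rule to retention.

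**Conclusion.** The point holds, at low severity, for two exploratory analyses; the co-primary analyses are untouched.

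(1) Read literally, the prediction question uses 30–50% of the Part 1 subjects, selected partly on the outcome. This raises the Fisher-z standard error from 0.19 to between 0.29 and 0.41. The attenuation from selection is real in direction, but its size rests on assumed windows.

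(2) The retention fraction cannot separate change from resampling. With 5 of 349 drugs called and no change, it is expected to be about 56–79% at r = 0.90 and 86–94% at r = 0.99 across the two score distributions tried. A figure in or near those ranges would not by itself show an effect of chemotherapy. These percentages illustrate the problem and do not predict this assay's performance.

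**What to change.** **Prediction.** Reword Section 2.3.1 so that predicted sensitivity to first-line therapy, taken from the first biopsy, is tested against first-line outcome in every Part 1 subject with a usable first biopsy and follow-up, whether or not that subject enters Part 2. Reserve the paired biopsies for the change question.

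**Change.** In Section 2.3.2, report lost and newly gained drugs together, add the rank correlation of all drug scores between the two biopsies, and record whether the sites match. Describe the result as change between biopsies. Attribute it to chemotherapy only if it exceeds whatever repeat-sample agreement is available. Put both analyses under Section 10.9.

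**Cost.** Mainly analysis wording, with no new visits or biopsies. Data must be linked from the Part 1 protocol, and the availability of first-line outcomes there should be confirmed. The documents show no repeat-biopsy agreement data; if none exist, the cautious description is the only one open. With 9 to 15 pairs, a formal split by site match is too thin to require, so recording it is enough.

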3. BACKGROUND & RATIONALE

3.1 Pancreatic Cancer

Pancreatic ductal adenocarcinoma (PDA) is a major health problem worldwide. It is predicted to be the 2nd leading cause of cancer-related death in the United States by 2030 and carries a dismal 5-year survival of 8.2% despite 50 years of research and therapeutic developments [1, 2]. During 2018, it is estimated that 55,440 people will be diagnosed with PDA and approximately 44,330 people will die from PDA in the United States [2].

Currently, surgical resection offers the only therapeutic means of cure. However, only 15-20% of patients have resectable disease. Even among the small subset of patients who are suitable for surgical resection at the time of diagnosis, complete resection is followed by recurrence in >90% of patients without further systemic therapy, with a median time to recurrence of 6.9 months [3]. In the metastatic setting, the 5-year overall survival is 2% [4]. Therefore, PDA is an unmet need that desperately requires better medical intervention.

Despite recent advances in systemic therapy, upfront cytotoxic chemotherapy for PDA has been disappointing with response rates of 20-30% for the most active regimens and no impact on the 5-year survival rate [5, 6]. The majority of patients will progress after a median of 5-7 months. Data from the second-line NAPOLI-1 study showed that 5-fluorouracil in combination with nanoliposomal irinotecan improved both median PFS and OS compared with 5-fluorouracil alone (3.1 vs 1.5 months and 6.1 vs 4.2 months, respectively) [7]. There is currently no standard-of-care treatment regimen available for the third-line setting, and consensus guidelines recommend best supportive care or participation in a clinical trial [NCCN 2018]. Thus all PDA patients require systemic chemotherapy, and more effective regimens are urgently needed [8].

3.2 Targeted Therapy in Pancreatic Cancer

For at least two decades, there has been an intensive focus on identifying and targeting specific mutations or pathways in PDA. The prevailing model has been that mutated oncogenic drivers are the ideal cancer drug targets (as epitomized by the responsiveness of c-Kit mutant GIST to imatinib). However, few such targets are present in PDA aside from mutant K-ras, which has proven pharmacologically intractable [9]. Indeed, best estimates suggest that only around 15% of PDA tumors harbor alterations that can be matched by current precision therapies. Moreover, many examples exist of tumors bearing targetable mutations that nonetheless fail to respond to

matched therapies and, conversely, of tumors that are unexpectedly sensitive to targeted drugs in the absence of a known relevant oncoprotein [10, 11]. For example, treatment of EGFR-mutant pancreatic tumors with the EGFR inhibitor erlotinib provides at best a modest benefit, despite substantial efficacy in lung cancer [12]. These observations imply that the signaling context of a mutation is highly relevant to therapeutic response. It is our **hypothesis** that the context itself–that is, the regulatory state of the tumor cell– is a relevant and promising therapeutic target (**Figure 2**).

A novel systems biology approach, developed by [name] (co-PI) at Columbia University Medical Center, is uniquely positioned to extend the frontier of personalized medicine for patients with treatment refractory cancers, including advanced PDA. The OncoTreat algorithm is able to prioritize potentially effective FDA-approved and investigational oncology drugs, on a patient-by-patient basis, for patients currently lacking effective treatment options. In this prospective study, we will investigate the feasibility of using OncoTreat to inform rational selection of off-label FDA-approved oncology drugs for patients with advanced PDA who have received one or two prior lines of systemic therapy.

Figure 2. Regulatory Network Concepts and OncoTreat Framework. A) *Regulatory Proteins* (e.g. transcription fractions, co-regulators, and others) are proteins that alter the transcript abundance of target genes. **B)** The collection of genes targeted by a regulatory protein is a *regulon*. Their relative abundances define the *activity* of a regulatory protein. C) A regulatory protein whose activity is altered during tumor development is a *Master Regulator (MR)* of malignancy. D) A *regulatory network* is a global compilation of regulatory genes and their targets (colored circles represent major Mastor Regulators of PDA). **E)** MRs occupy critical nodes within signaling networks. While many upstream signaling molecules may acquire oncogenic mutations, they must ultimately affect the activity of a limited set of MRs that effect execution of their function. **F)** The MRs that promote or restrain malignancy in an individual patient's tumor are identified from an expression profile using the VIPER algorithm. Similarly, the MRs altered by treatment with a drug are identified through high throughput RNA-sequencing of human PDA cell lines. The OncoTreat framework functions identifying drugs whose activity specifically affects the MRs of an individual patient. That is, drugs that inhibit the patient's positive cancer MRs and activate the patient's negative cancer MRs.

